We will consider criteria for success as the proportion of persons who made an emergency call to an adult, teacher, the emergency number of the regional hospital, to a medical professional or to the closest Health Facility to the incident. The proportion of people who received help. The proportion of persons whose bleeds or LTBs were alleviated or attended to or who were referred for better management. Furthermore, the intention to treat/carryout the desired first aid act in the phase of an acute incident requiring FA. Lastly, we would like to evaluate the number of students who perform well during the scenarios to evaluate the need for knowledge revamping/refresher course on the aspects of FA taught. And all these, we shall compare the outcomes between the intervention and control groups.

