3.8 DATA COLLECTION TOOLS

A) Questionnaire

**Pre- and Post-Implementation of a Young First Aiders (YoFA) Training
Program Amongst Early Secondary School Children on Injury and Trauma
First Aid in Fako Division.**

Health District _____
Secondary School _____

Date: _____
Class: _____

A) QUESTIONNAIRE

Section 1

Please answer the questions below by **ENCIRCLING OR WRITING** the right answer you think is correct. If you do not know an answer, please select the answer you think is correct.

1. Gender	YES	or	NO
2. Age (in years):	_____		
3. Parents' Occupation:	Father _____ Mother _____		
4. Do you have access to a mobile phone all the time?	YES	or	NO
5. Have you heard the words First Aid?	YES	or	NO
6. Have you ever seen a traumatic injury? (A traumatic injury is an injury you sustain when something outside your body causes you to lose function or render you unable to use part or all of your body because of pain, bleeding or the because it is very serious)	YES	or	NO
7. A) Have you ever received any training in First Aid (formal or informal)?	YES	or	NO
B) If yes, briefly describe the training (where was it, what did you learn? How long ago was it?)			
Where? _____			
How long ago?			

 a) < 6months ago b) 6 to less than 12 months ago c) 1 to 3 years ago d) >3 years ago 			
What you learnt? _____			
<hr/>			
8. Have you ever seen someone bleeding and tried to stop that bleed yourself at home, school, marketplace, or anywhere else?	YES	or	NO
B) How many times has that happened? (Choose one)			

 a) Never b) Just once c) 2 to 5 times d) >5 times 			

C) What did you do to stop the bleeding? _____ **YES** or **NO**

D) Did it work? **YES** or **NO**

9. **A) Do you remember watching other people do this in the past?** **YES** or **NO**
B) Have you ever watched someone else offer such help in question 5? **YES** or **NO**

10. **If you find someone bleeding today,** **YES** or **NO**

A) Will you help them?

B) If 'no', why will you not help?

- I don't know what to do
- I am afraid I will make it worse
- I am afraid I will get into trouble
- I am afraid of blood
- Other reason _____

C) If 'yes', why will you help? _____

D) What steps will you take to help if 'yes'?

- Help by putting in toothpaste
- Help by applying pressure on the wound
- I will not help
- I will call an elderly person.

[figure not shown]
B) If you would not help, what makes you not want to help?

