A tourniquet is a device that, when properly applied, stops blood from flowing by compressing blood vessels to a bone. [representative photos of a commercial Combat Application Tourniquet and an improvised tourniquet, both placed on a forearm]

26. **A tourniquet can be applied to a LTB in which of the following areas? (More than one answer)**

- Leg
- Arm
- Hand
- Stomach

27. **Which of the following need a tourniquet applied to save the life (one answer ONLY):**

- Scrape/scratch from a fall
- full-thickness burn
- Cut to thigh
- Spurting blood from leg

28. **A tourniquet may be required for an arm/leg that is partially or fully torn off.**

- a) True
- b) False

This next section is about the actions of using pressure and tourniquets to stop LTB.

29. **Climbing over a fence, a person cuts their stomach; it is bleeding and 3-4 inches (7-10cm) long. To control bleeding from this wound, you should:**

- a) Apply firm pressure with your hand directly where the bleeding seems to be coming from
- b) Apply a pressure dressing first, then apply manual pressure over the pressure dressing
- c) Apply an elastic bandage around the abdomen, ensuring that the wound is covered
- d) Apply a cold pack to the wound

30. **If you are alone with somebody who is not awake and has LTB coming from an arm/leg, what best describes your first action(s)?**

- a) Call for help on a cell phone
- b) Put a tourniquet on the injury
- c) Call for help while apply pressure or placing a tourniquet (i.e., speaker phone, yelling, activating alarm)

31. **Put the tourniquet above the wound so that it is between the torso/body and the wound.**

- a) True
- b) False

32. **After placing the tourniquet above the injury, it is critically important to tighten it as much as possible before turning the stick/rod.**

- a) True
- b) False

33. **You have applied a tourniquet to a LTB on a leg. The bleeding appeared to stop initially, but has now restarted. Which of the following should be the next step:**

- a) Apply a second tourniquet above the first (between the first tourniquet and the torso)
- b) Check to see if the tourniquet has loosened and tighten the tourniquet by turning the windlass/rod more
- c) Loosen the tourniquet, then reapply closer to the wound
- d) Remove the tourniquet completely and apply a different type of tourniquet
- e) Apply a second tourniquet directly on top of the first tourniquet

34. **If the person is in pain, the tourniquet is on too tight.**

- a) True

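### Section 1 of the questionnaire asks for the correct answer to items that have none, item 10D has no response rule, and item 9B points to the wrong question

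*Protocol*

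**What the plan says.** All of the wording at issue is in Protocol section 3.8, part A (Questionnaire).

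- **Instruction.** At the head of Section 1, pupils are told to encircle or write "the right answer you think is correct", and then: "If you do not know an answer, please select the answer you think is correct". Section 1 runs from item 1 to item 18, and no item is exempted.
- **Items under it.** Besides background items, these include experience (items 5 to 9; item 8 asks "Have you ever seen someone bleeding and tried to stop that bleed yourself at home, school, marketplace, or anywhere else"), willingness (item 10A, "A) Will you help them", with reasons in 10B and 10C), motivation (item 12) and knowledge (items 13 to 18).
- **Item 10D.** The stem begins "What steps will you take to help if" and is addressed to pupils who answered yes. The options are toothpaste, pressure on the wound, not helping, and calling an elderly person. No response rule is printed. Items 8B and 27 ask for one answer; items 12 and 26 allow several.
- **Item 9B.** It asks "Have you ever watched someone else offer such help in question 5". Question 5 asks whether the pupil has heard the words first aid.

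The answers feed the aims. Section 1.6.2 (objective 2) glosses attitudes as willingness. Section 3.9 collects helping behaviour (attitude) with the pre- and post-test questionnaires. Section 3.6, Step 3, lists the intention to carry out first aid among the criteria compared between groups. Section 3.11 analyses change in knowledge, attitudes and practices by difference-in-difference.

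**The concern.** Whether a pupil has tried to stop a bleed, would help, or is moved by family or friends is a matter of fact or disposition. Asking for the right answer invites the pupil to report what is approved of. At pretest that cue falls on both arms alike. At post-test one arm has just been taught that responding to a bleed is what is wanted, so the same cue may pull harder there. A difference-in-difference would read the extra pull as programme effect.

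Item 10D has a separate fault. If the form does not say whether several options may be marked, one mark has more than one meaning, and no later scoring rule can recover which was intended. Item 9B sends the pupil to a question in which no help is described.

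**Working it through.** **1. What the plan quantifies.** It gives no figure for response bias. The only yardstick is the difference in section 3.5, 0.50 against 0.75. For two proportions, two-sided alpha 0.05 and power 0.80, with mean proportion 0.625:

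n = [1.960 × √(2 × 0.625 × 0.375) + 0.842 × √(0.50 × 0.50 + 0.75 × 0.25)]² / 0.25² = (1.342 + 0.557)² / 0.0625 ≈ 57.7, so 58 per group, as stated. This figure is context only and is not disputed here.

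**2. When the instruction biases the comparison.** Let b be the amount by which the wording raises the proportion answering yes, in the trained (T) or control (C) arm, before (0) or after (1). The bias in the difference-in-difference is

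(bT1 − bT0) − (bC1 − bC0).

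- If b is the same throughout, or changes equally in both arms, the bias is 0.
- If b rises only in the trained arm, the bias is that rise, in favour of the programme.

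**3. How large it could be (assumption, not a finding).** Only pupils who would otherwise say no can be moved. With baseline willingness p, and an extra share s of unwilling trained pupils (beyond controls) answering yes, the spurious difference is s × (1 − p):

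| p | s = 0.10 | s = 0.20 | s = 0.30 |
|---|---|---|---|
| 0.50 | 5 points | 10 points | 15 points |
| 0.70 | 3 points | 6 points | 9 points |
| 0.80 | 2 points | 4 points | 6 points |

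Neither p nor s is in the protocol. Part of s would also remain under neutral wording, because self-report by pupils who know they were trained is open to social desirability in any case. The part due to the instruction is therefore smaller than s and cannot be separated from the documents.

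**4. Item 10D.** Section 3.3.2 names both calling for help and stopping a bleed as the focus. Section 3.6, Step 3, counts "the proportion of persons who made an emergency call to an adult" as success and also counts bleeds attended to. Item 30 joins the two actions in one option: "Call for help while apply pressure or placing a tourniquet". The plan thus treats them as compatible. A pupil who ticks only one on 10D may mean that action alone, or may intend both and believe that one mark is allowed. The two cases give the same record. A pupil who ticks the refusal option contradicts the stem.

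**5. Item 9B.** Question 5 concerns having heard a term. Question 8 concerns trying to stop a bleed. Only question 8 describes help that could be watched.

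**The case against.** The strongest reply is that both arms read the same instruction at every test, so a constant effect cancels, and that any tendency of trained pupils to say yes is ordinary social desirability. The first part stands, and step 2 shows it. The second stands in part: the instruction does not create the tendency, but it adds a needless cue that only the trained arm has been taught to read.

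A reader might infer that attitude change is shown to be biased towards the programme, or that a given percentage of pupils answering yes for this reason overstates the effect by as many points. The documents support neither. The direction is a reasoned risk, and only otherwise unwilling pupils in excess of controls count.

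A reader might also infer that 10D forces a choice between two taught actions and marks right behaviour as wrong. The plural in the stem permits several marks, no single-choice rule is printed, and no scoring key is shown; a key may be in the analysis plan. A key accepting pressure alone would lower the measured effect, the opposite direction to the instruction problem.

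Item 10 is not the whole attitude measure, and none of the five outcome variables in section 3.7 is the willingness item. Section 1.1.2 adds a Likert survey of intent and a self-efficacy scale. However, the survey is described only after training, so it offers no pretest, and the scale measures confidence rather than willingness.

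Finally, the abstract says the questionnaires are self-administered, while sections 3.10 and 3.12 have data collectors administer them. Collectors could soften the instruction, but nothing says that they will.

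**Conclusion.** The point holds as a fault in the form. The instruction does not fit items 5 to 9, 10A to 10C and 12, and it risks inflating the change in willingness. Its size is unknown. It is zero if both arms shift equally; the 2 to 15 points in the table rest wholly on assumed values of baseline willingness and of the extra share, and should not be read as an estimate. Item 10D as printed yields single ticks that cannot be interpreted, and item 9B carries a wrong cross-reference. These two need no assumption about bias, and neither can be repaired at analysis. Correction is worthwhile because it is cheap and the items serve the stated pre/post aims; it does not by itself put the trial's conclusions in doubt.

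**What to change.** Before the first pretest, on paper and in the Kobo version alike:

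1. Over the factual, experience, willingness and motivation items (1 to 12, subject to point 3 for 10D), print a line such as: these questions have no right or wrong answer; tell us what is true for you. Keep the correct-answer line for the knowledge items.
2. Mark 10D to allow all options that apply, and remove the option of not helping, which 10A and 10B already capture.
3. Have the sponsor decide whether 10D is descriptive or scored. If it is scored, fix the rule in advance, consistently with sections 3.3.2 and 3.6 and with item 30, and do not place it under the neutral line.
4. In 9B, change the reference from question 5 to question 8.

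The cost is a few lines on the form. The same version should serve both arms at pretest, immediate post-test and three months.

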3.3.1 Qualitative Part

Discussions or interviews on perspectives of individuals and groups of individuals regarding the acceptability and usability of FA-trained kids within the school and in the community. It will also seek to understand their thoughts on incorporating an FA training program within the school curriculum. It will be conducted with key stakeholders, including school administrators, and community leaders as well as students of the school.

It will precede the qualitative part and include Focused group discussions (FGDs), in-depth interviews of certain community and administrative stakeholders within the school and observations of scenarios.

3.3.2 Quantitative Part:

The quantitative aspect will involve administering questionnaires to students to assess their knowledge, attitudes (confidence), and practices (utilisation/usability) of FA trauma/injury skills before and after their training. This will focus mostly on staying safe, calling for help and stopping a life-threatening bleed. The intervention will include training the intervention group in reasonable clusters on the same subject matter and assessing the change in KAPs before and after the intervention. It will also include scenarios to test the efficacy of participants in carrying out the First Aid Act.

PERIOD OF STUDY

The study will be a 10-month study from September 2024 to July 2025 including administrative and ethical clearance needed.

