will be a session for pretesting at the beginning of the intervention, at the immediate end, and 3 months after. **During the 3 months follow up period, we will visit the schools during their Wednesday club days every 2 weeks for 30mins to 1hour, to document their experiences and challenges in real time and their use of the skills.**

The qualitative part will take place before the quantitative pretesting of both groups begins.

Table 6: Plan of training and Evaluation of intervention groups

HA	School	N	Training Period in 2024	Date for Last Evaluation, 2024
Molyko (Intervention)	BGS Molyko	25	Nov 6 th , and 13 th	Feb 5 th
		25	Nov 20 th , and 27 th	Feb 19 th
		25	Dec 4 th and 11th	March 5 th
Mutengene (Control)	GHS Mutengene	70	November 6 th	Feb 26 th
	Total	145		

Step 3: Evaluation Phase

This comprises the evaluation of students' perceptions, barriers, and challenges in learning and applying the skills and lessons learned. It will equally involve evaluating parents' and stakeholders' perceptions about the program and including FA training in school curricula. It will involve the use of evaluation forms. This will take place about the same time as the post-three-month evaluation.

Knowledge will be assessed by evaluating whether the participants have ever heard of first aid or observed situations in which first aid was needed. They will be expected to have an increase in knowledge of first aid, especially regarding calling for help, stopping acute and life-threatening bleeds (LTB), and referrals after the training.

Before the training, we expect people not to have practiced first acts ever or to have

done it in a wrong way or to be scared to carry out specific first aid acts. After the training, we expect them to be more alert and identify situations needing first aid acts. Additionally, we expect their self-efficacy and confidence to perform first aid acts to increase and to effectively carry out first aid acts within their community or the school premises that will be documented using designed forms.

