3.7 STUDY VARIABLES AND TYPE

Variables

Outcome variables

1. Knowledge Change: to determine whether or not there was an overall change in knowledge before and after the training (dichotomous).
2. Test scores: to measure the educational efficacy of the first aid training before and after the intervention in comparison with the control group (continuous)
3. Self-efficacy ratings: Participants' self-perceived efficacy in performing first aid skills or their confidence levels in "Stopping the bleed and/or calling for help" (dichotomous)

4. Response time: The time taken by participants to respond to simulated first-aid scenarios or emergencies that require them to either stop an LTB or call for help or refer (continuous).
5. The number of participants who make use of the skills taught during the 3 months post-training but before the final assessment (Discrete).

Exposure Variables

The exposure variables include training on LTBs from injury first aid and the use of these services by the trained students (e.g., the number of persons assisted or referred during the follow up period of the training).

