3.11 DATA ANALYSIS PLAN

A difference-in-difference analysis would be done to assess the change in KAPs before and after the intervention in. The posttest would be done immediately after the 4 days of training for each pool and 3 months after the training to assess the need for refresher course planning.

The exposure variables include training on LTBs from injury first aid and the use of these services by the trained students (e.g., the number of persons assisted or referred during the follow-up period of the training).

We will analyze survey data using R Software with a combination of descriptive statistics and parametric and non-parametric tests to establish statistically significant differences between pre- and post-test results and between the intervention and control groups.

Table 7: Objectives and their Indicators

Objective	Activities/process	Data collection tools	Data Source	Indicators
1. To understand the perspectives of stakeholders on YoFA training program among SSC	- In-depth interviews	-In-depth interview guides	School teachers, administrators, parents, community leaders and students	
2. To assess school children's KAP (willingness and self-efficacy on trauma/injury FA via the built YoFA training to stop LTBs.	- survey	-Questionnaire	- students	- Obtain baseline KAP Scores
3. To evaluate the effectiveness and usability of the YoFA training program for SSC to respond to LTBs safely and promptly in their environs.	-Training following a specific STB and LFRs program -Training students on specific modules of LTB FA - Pre and post test -Simulation exercises	- Use adapted tools from the SBEAT - Questionnaires - Evaluation form with questions how? What was the situation?where, and how?	Stakeholders, teachers, parents, students	- Change in knowledge scores -At least 50% of stakeholders rate the program as good/ expectations met - 70% of students rate the program as good/expectations met - Number of children who made use of the FA skills taught
4. To determine the barriers associated with implementing the YoFA program among early SSC in the Fako Division.	- Interviews - Survey	-Interview guides - Questionnaires	- Stakeholders, - Teachers, students	- Perceived reasons and challenges that hinder FA training in schools.

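### The only questionnaire items on actual first aid practice ask about lifetime experience, so a pre/post difference-in-difference built on them would misstate the change in practice

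*Protocol*

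**What the plan says.** Section 3.8 prints a single form, titled "Pre- and Post-Implementation of a Young First Aiders (YoFA) Training" programme. Item 8 asks "Have you ever seen someone bleeding and tried to stop that bleed yourself". 8B asks how often, in four bands (never, once, two to five, more than five). 8C and 8D ask what was done and whether it worked. None of these has a recall window.

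Section 3.3.2 says questionnaires are given before and after training to "assess their knowledge, attitudes (confidence), and practices (utilisation/usability) of FA" skills. Section 3.6 sets the occasions: for the control group there "will be a session for pretesting at the beginning of the intervention, at the immediate end, and 3 months after". Section 3.11 states: "A difference-in-difference analysis would be done to assess the change in KAPs".

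Outcome 5 in Section 3.7 is time-limited: "The number of participants who make use of the skills taught during the 3 months post-training but before the final assessment". Section 3.6 also provides fortnightly school visits during follow-up and designed forms on which first aid acts are recorded. Table 7 lists an evaluation form and, as an indicator, the number of children who used the skills.

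**The concern.** Hypothesis 3 (Section 1.6.2) includes an improvement in practice, and Section 3.11 would test it as a change over time between two schools. That needs a measure that can change over the interval. A lifetime yes/no answer, given truthfully, can only stay the same or go from no to yes. A pupil already at yes at the pretest adds nothing to the measured change, however often he or she helps after training.

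The other printed items do not fill the gap. Item 9 is about watching other people and item 10 about intention. Items 13 to 18 cover imagined situations and calling for help, and items 19 to 37 test knowledge of bleeding control. At stake is whether the practice part of the pre/post comparison can be read at all. The knowledge and attitude items are not touched.

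**Working it through.** **1. The plan's own figure.** The protocol states no effect size or baseline rate for item 8. The only effect it sizes is in Section 3.5: 0.50 against 0.75, two-sided 5%, 80% power, 58 per group. Check: n = [1.960·√(2 × 0.625 × 0.375) + 0.842·√(0.5 × 0.5 + 0.75 × 0.25)]² / 0.25² = (1.342 + 0.557)² / 0.0625 ≈ 57.7, so 58. It reproduces. Section 3.5 does not tie these proportions to practice, so they serve below only as a scale.

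**2. Equal baselines.** Let b be the share answering yes at the pretest and p the probability of trying to stop a bleed during follow-up. Assume that later use is independent of the baseline answer and that answers are truthful.

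- Share answering yes at follow-up: b + (1 − b)p.
- Change within an arm: (1 − b)p.
- Difference-in-difference with b equal in both arms: (1 − b)(p₁ − p₀).

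| Assumed b | True 20 points reads as | True 25 points (0.50 v 0.75) reads as | Power at 58 per group for the latter |
|---|---|---|---|
| 0 | 20 | 25 | 0.80 |
| 0.1 | 18 | 22.5 | 0.73 |
| 0.3 | 14 | 17.5 | 0.57 |
| 0.5 | 10 | 12.5 | 0.41 |

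The power column compares the two follow-up proportions, for example 0.65 against 0.825 at b = 0.3. It is illustrative only.

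**3. Unequal baselines.** The contrast becomes (1 − b₁)p₁ − (1 − b₀)p₀, with 1 the intervention school and 0 the control school. All values here are assumed.

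- No training effect, p₁ = p₀ = 0.20: the contrast is 0.20 × (b₀ − b₁). With b₀ = 0.5 and b₁ = 0.3 it shows a false benefit of 4 points; with the shares exchanged, a false harm of 4 points.
- True effect of 20 points, p₁ = 0.40, p₀ = 0.20, b₁ = 0.1, b₀ = 0.5: 0.9 × 0.40 − 0.5 × 0.20 = 0.36 − 0.10 = 0.26, which is more than the truth.

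The arms are one school each in two districts (Table 5), so equal b cannot be taken for granted. Table 1 gives average trauma counts of 1280.5 for Tiko (control) and 487.75 for Buea (intervention). These are counts, not rates, and only hint that exposure differs.

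**4. The count in 8B.** A pupil can move from once to two-to-five, so some new acts do show. Going from two to four acts does not show, and more than five is a ceiling.

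**5. The immediate post-test.** Table 6 puts the two training days a week apart (6 and 13 November for the first group), with the pretest on day 1. There is about one week in which any new act could occur.

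**The case against.** The strongest reply is that the protocol never names item 8 as the practice endpoint. Section 3.7 does not list it among the five outcomes. Section 1.6.2 glosses practices as self-efficacy, and Section 3.9 names knowledge, practical skills and helping behaviour. Item 8 stands beside age, parents' occupation and earlier training, so it may be background, and which items form a practice score may be left to a statistical analysis plan. This stands as a limit: the dilution applies only if item 8 feeds the comparison. It does not remove the point. Section 3.3.2 assigns practice, in the sense of utilisation, to the questionnaire, and no other printed item records what a pupil has done.

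A reader might infer three stronger things that the documents do not support.

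- That pupils at yes cannot show any new use. 8B can register it across bands, and 8C and 8D could show a change in technique, though undated.
- That outcome 5 is itself diluted. Visits, designed forms and the Table 7 evaluation form are other sources for it. What remains open is which of them supplies it and whether the visits cover both arms alike, since the sentence on visits sits under the control group.
- That the bias always runs toward no effect. Step 3 of the working shows otherwise.

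It is also fair that b may be small: Section 3.6 expects pupils not to have practised first aid before, or to have done it wrongly or been afraid to.

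**Conclusion.** The point holds in a limited form. Item 8 with 8B to 8D is the only printed pre/post measure of actual practice, and it is a lifetime measure. If it feeds the difference-in-difference, the yes/no contrast is diluted by (1 − b) when the schools share the same b, and can be biased in either direction when they do not. The size is unknown because the protocol gives no b: slight at 10% (20 points read as 18), substantial at 50% (20 read as 10).

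The factor rests on truthful answers and on later use being independent of the baseline answer. If the two are related, the factor instead multiplies the difference among pupils who said no at baseline. It would go too far to call the trial underpowered on this ground, since the sample size is not tied to this item. The wording should nonetheless be settled in the instrument, because a later analysis plan cannot recover a time window that was never asked.

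**What to change.** Keep the existing item 8 as a description of pupils at baseline. Add to the pretest and to the 3-month test, identically in both arms, a question with one fixed window, such as: *In the last 3 months, how many times did you see someone bleeding, and how many times did you try to stop it?* Base the practice difference-in-difference on that question. The same window on both occasions keeps the planned analysis intact, lets the answer fall as well as rise, and separates opportunity from action.

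Do not analyse change in practice at the immediate post-test. State one source for outcome 5 and apply it alike in both arms.

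The cost is one or two more questions on the form. Recall over three months at ages 10 to 14 will be imperfect, but it is asked in the same way in both schools.

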- **Streaming:** run or flow in a continuous current in a specified direction
- **Oozing or Trickling:** For a small amount of liquid to flow slowly out of something through a small opening or hole
- **Gushing:** flowing out suddenly, forcefully, or in large volume, as fluid that has been confined

[figure not shown]
This section is about being able to identify LTB (Life Threatening Bleeding) from a variety of descriptions (You can choose more than one answer)

19. Which of the following need immediate first aid to stop the bleeding:

a) Illustration of Blood oozing from scraped/scratched knee

b) Illustration of Blood spurting from arm

c) Illustration of Blood pooling on the ground

d) Illustration of Blood gushing from amputated foot

20. Which of the following does not need immediate first aid to stop the bleeding:

- a) Spurting/pulsating blood from the injury
- b) Streaming blood from the injury
- c) Oozing/trickling blood from injury
- d) Gushing blood from the injury

21. Which of the following need immediate first aid to stop the bleeding:

a) Photo of Scrape from a fall

b) Photo of full-thickness burn

c) Photo of Cut to thigh

d) Photo of Spurting blood from a forearm

22. Which of the following need immediate first aid to stop the bleeding:

- a) Blood spotting through one piece of gauze
- b) Blood-soaked clothing or bandages
- c) Bleeding that is not soaking through a bandage
- d) The overlying clothes are soaked in blood

23. Which of the following need immediate first aid to stop the bleeding:

- a) Pooling of blood on the ground
- b) Enough blood to fill 1/2 a soda can
- c) Two-tablespoons of blood from the injury on the ground
- d) A hole in the skin without flowing blood

24. **Which of the following need immediate first aid to stop the bleeding:**

- Dripping blood from a cut
- Gushing blood that will not stop coming out, even with a hand pushing on it
- Flowing blood from an injury that you are pressing on
- Blood spotting through several layers of cloth

25. **Rank the following: 1= at the top, most likely to die-- 4= at the bottom least likely to die**

- Bleeding from a person who is now unconscious
- Bleeding from a person who is not alert/not fully awake anymore
- Bleeding from a person who is now confused/not acting normally
- Bleeding from a person who is now pale

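### Ranking item 25 is printed in its apparent answer order with a top-to-bottom cue, so pupils can rank it correctly without knowledge, which may slightly weaken the measured training effect

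*Protocol*

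**What the plan says.** The questionnaire in Protocol section 3.8 is headed as both the pre- and the post-implementation form. Item 25 reads "Rank the following: 1= at the top, most likely to die-- 4= at the bottom least likely to die". Its options appear in this order:

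1. "Bleeding from a person who is now unconscious"
2. "Bleeding from a person who is not alert/not fully awake anymore"
3. "Bleeding from a person who is now confused/not acting normally"
4. "Bleeding from a person who is now pale"

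Nothing says that these options are shuffled. The form's other ordering task, item 13, does tell pupils that its pictures are jumbled. The opening instruction asks pupils to choose an answer even when they do not know it.

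Item 31 is a true/false statement: "Put the tourniquet above the wound so that it is between the torso/body and the wound". The next item begins from that placement: "After placing the tourniquet above the injury, it is critically important to tighten it as much as possible before turning the stick/rod".

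Section 3.7 lists a continuous test score, compared before and after training and with the control group, as outcome variable 2. Section 3.11 plans a difference-in-difference analysis. Testing takes place before training, immediately after it and three months later (sections 3.6 and 3.11). The protocol prints no answer key, no scoring rule and no item results from piloting.

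**The concern.** An item in a knowledge test should be hard to get right without the knowledge. In item 25 the list order and the stem's positional words point to the same response, so numbering down the list earns the credit. On the completed form that response looks the same as an informed one.

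If some pupils do this, the pretest and control scores include credit that knowledge did not earn. A trained pupil who would have ranked correctly anyway by following the cue shows no gain on the item. The arm contrast then shrinks towards zero, and the baseline level used for Hypothesis 2 (limited knowledge) is slightly too high. Judging the severity of bleeding is core content of the programme, so the item is worth having in working order.

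**Working it through.** **Plan's own figures.** The protocol gives no figure for the test score that could be reproduced. Its only related design figure is the sample size in section 3.5. Proportions of 0.50 and 0.75, two-sided 5% and 80% power give 58 per group and 116 in total before dropout. This reproduces with the standard two-proportion formula, and the present point does not affect it.

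**Reading the item.** The stem assigns 1 to the top and to the greatest risk of death, and 4 to the bottom and the least. The printed states run from unconscious through not alert and confused to pale. The apparent key is therefore 1-2-3-4 from top to bottom. This is inferred from the stem and the options, because no key is printed.

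**Chance of a correct answer without knowledge.** Four options can be ranked in 4! = 24 ways, so a random ranking is right 1/24 = 4.2% of the time. Let d be the share of pupils without the knowledge who number down the list. Then P = d + (1 − d)/24.

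**Effect on the gain.** Let true knowledge in the trained arm rise from k0 to k1, with no change in the control arm and the same d at every test and in both arms. The observed proportion correct is k + (1 − k)P. The difference-in-difference on the item is then (k1 − k0)(1 − P). Without the cue it is (k1 − k0)(23/24). The loss is d × (23/24) × (k1 − k0).

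Assumed values are k0 = 0.20, k1 = 0.60 and d from 0.3 to 0.8. Without the cue the gain is 0.40 × 23/24 = 0.383.

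| d (assumed) | P | Gain with cue | Loss (items) | Loss, 25-item score |
|---|---|---|---|---|
| 0.3 | 0.329 | 0.268 | 0.115 | 0.46 points |
| 0.5 | 0.521 | 0.192 | 0.192 | 0.77 points |
| 0.8 | 0.808 | 0.077 | 0.307 | 1.23 points |

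The last column is loss/25 × 100, in percentage points of an equally weighted score. The 25 items are 13 to 37, which look scorable, but the protocol does not define the scored set. The loss is proportional to k1 − k0, so if the true rise were half as large, every loss would halve.

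**Outer bound for item 25.** Suppose that untrained pupils would otherwise rank purely at random and that every trained pupil is right. The loss is then d × (1 − 1/24) = 0.958d items:

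- d = 0.10: 0.096 items, or 0.4 points of 25 items (0.5 if only items 19 to 37, that is 19 items, are scored)
- d = 0.50: 0.479 items, or 1.9 points (2.5 of 19)
- d = 1.00: 0.958 items, or 3.8 points (5.0 of 19)

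**Items 31 and 32 (conditional).** A guesser is right on item 31 half the time. If a share c of pupils without the knowledge use the wording of item 32, P = c + (1 − c)/2. With c = 0.2, 0.5 and 0.8 (assumed), P = 0.60, 0.75 and 0.90. For the same rise from 20% to 60%, the gain is 0.40 × (1 − P) = 0.16, 0.10 and 0.04, against 0.20 without the cue. The largest combined loss in these assumed ranges is 0.307 + 0.16 = 0.47 of an item. If every pupil used both cues, untrained pupils otherwise guessed and all trained pupils were right, it would be 23/24 + 1/2 = 1.46 items.

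**The case against.** The strongest objection is that cue use is conjecture. A reader might infer that untrained pupils do score these items as correct and that the gain is understated. The documents do not support that as fact: there is no key, no scoring rule and no pilot result, and every usage rate above is assumed. This stands, and the point is limited to what the layout allows.

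The fielded layout is also uncertain. The abstract describes self-administered questionnaires, and the form tells pupils to circle or write. Section 3.10 has interviewers using Kobo, and the risk table in section 3.12 has data collectors giving the tests. Shuffling in Kobo is neither stated nor excluded. The picture items carry text placeholders, so the printed form may not be exactly what pupils see. This stands as a reason to check the fielded version. It does not remove the fault, because the cue in item 25 lies inside the item and works on paper, on screen or read aloud unless the order is changed.

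A reader might also treat items 31 and 32 as an equal fault. They are not. Item 31 comes first, so the cue works only if a pupil sees both items, goes back, or remembers item 32 at a later test. Item 31 also has a 50% guess rate.

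It is tempting to say that 30% to 80% of the effect on item 25 is lost. Those ratios only restate the assumed cue use. The random-ranking comparator is probably too harsh as well, since many untrained pupils of 10 to 14 may sense that unconsciousness is worst.

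Finally, the damage is not beyond repair, since the item can be left out of the score. Nor does it favour the programme: with equal cue use in both arms it cannot produce a false positive.

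**Conclusion.** The point holds as a minor fault in the instrument. Item 25 can be ranked correctly by numbering down the list. That can raise baseline and control scores and slightly weaken the difference-in-difference in test scores. On the assumed ranges the loss is about 0.5 to 1.2 percentage points of a 25-item score. The outer bound is 3.8 points, if every pupil without the knowledge followed the cue and nobody untrained had any idea of the order.

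The conclusion rests on the inferred key, one mark per item, the same cue use at each test and in both arms, and the options being shown in the printed order. The wording of items 31 and 32 is a secondary matter whose effect depends on how the form is administered. The sample size is unaffected, and the point takes no position on which first-aid answers are right.

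**What to change.** Before the pretest:

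- Print, or show in Kobo, the four options of item 25 in one fixed scrambled order, for example confused, unconscious, pale, not alert. Use the same order in both arms and at all three tests.
- Replace the stem by: *Write 1 next to the person most likely to die and 4 next to the person least likely to die.*
- Reword item 32 so that it asks about tightening before the rod is turned and no longer states where the tourniquet sits.

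If pretests have already been taken on the present form, keep them and report the between-arm score with and without item 25. Do the same for item 31 if the form was self-administered.

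The work is a few lines of editing, with no change to sample size or design. The cost is a slightly lower baseline score and a small further departure from the source tool, which section 3.9 already describes as adapted.
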